Gastrointestinal toxicity (cont.)	
Colitis, Grade 4	
 • Permanently discontinue atezolizumab and cobimetinib, and contact Medical Monitor.^a • Initiate supportive care and monitor patient closely. • Discontinue medications that may exacerbate colitis (e.g., NSAIDs). • Refer patient to gastrointestinal specialist for evaluation and confirmatory biopsy. • Initiate treatment with 1–2 mg/kg/day IV methylprednisolone or equivalent and convert to 1–2 mg/kg/day oral prednisone or equivalent upon improvement. • If event does not improve within 48 hours after initiating corticosteroids, consider adding an immunosuppressive agent. • If event resolves to Grade 1 or better, taper corticosteroids over ≥ 1 month.

IV=intravenous; NSAID=non-steroidal anti-inflammatory drug.

^a Resumption of atezolizumab may be considered in patients who are deriving benefit and have fully recovered from the immune-related event. Patients can be rechallenged with atezolizumab only after approval has been documented by both the investigator (or an appropriate delegate) and the Medical Monitor.

Table 6 Guidelines for Management of Patients Who Experience Specific Adverse Events (Cobimetinib and Atezolizumab) (cont.)

Event	Action to Be Taken
Dermatologic toxicity	
General guidance	
 • A dermatologist should evaluate persistent and/or severe rash or pruritus. A biopsy should be considered unless contraindicated.
Dermatologic event, Grade 1 or 2	
 • Continue atezolizumab and cobimetinib. • Initiate supportive care (e.g., antihistamines, topical corticosteroids). If event does not improve, consider treatment with higher-potency topical corticosteroids. • For Grade 2 rash, consider referral to dermatologist. 
Acneiform rash:
 
 • Consider topical corticosteroids (e.g., hydrocortisone 2.5%, alclometasone) and oral antibiotics (minocycline, doxycycline, or antibiotics covering skin flora) as clinically indicated.

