Dermatologic event, Grade 3	
 • Withhold atezolizumab and cobimetinib. • Refer patient to dermatologist. A biopsy should be performed if appropriate. • Consider initiating treatment with 10 mg/day oral prednisone or equivalent, increasing dose to 1–2 mg/kg/day if event does not improve within 48–72 hours. • If event resolves to Grade 2 or better within 105 days, resume atezolizumab at fixed dose. If not, permanently discontinue atezolizumab and cobimetinib.^{a, b} • Permanently discontinue atezolizumab and cobimetinib and contact Medical Monitor if event does not resolve to Grade 1 or better within 105 days.^{a, b, c} • If event resolves to Grade 2 or better within 28 days, resume cobimetinib with dose reduced by one level. If not, permanently discontinue cobimetinib. 
Acneiform rash:
 
 • Consider continuation of topical corticosteroids (e.g., 2.5% alclometasone) and oral antibiotics (e.g., minocycline, doxycycline, or antibiotics covering skin flora) when restarting cobimetinib.
Dermatologic event, Grade 4	
 • Permanently discontinue atezolizumab and cobimetinib, and contact Medical Monitor.^c

^a If corticosteroids have been initiated, they must be tapered over ≥ 1 month to ≤ 10 mg/day oral prednisone or equivalent before atezolizumab can be resumed.

^b Atezolizumab may be withheld for a period of time beyond 105 days to allow for corticosteroids to be reduced to ≤ 10 mg/day oral prednisone or equivalent. The acceptable length of the extended period of time must be agreed upon by the investigator and the Medical Monitor.

^c Resumption of atezolizumab may be considered in patients who are deriving benefit and have fully recovered from the immune-related event. Patients can be rechallenged with atezolizumab only after approval has been documented by both the investigator (or an appropriate delegate) and the Medical Monitor.

Table 6 Guidelines for Management of Patients Who Experience Specific Adverse Events (Cobimetinib and Atezolizumab) (cont.)

Event	Action to Be take
Elevations in ALT, AST, and/or bilirubin	
AST/ALT >ULN to $\leq 3 \times$ ULN with total bilirubin < $2 \times$ ULN (Grade 1)	
 • Continue atezolizumab and cobimetinib. • Continue with the standard monitoring plan (i.e., LFTs Q4W before dosing).

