AST/ALT > $3 \times$ baseline values to < $5 \times$ ULN with total bilirubin < $2 \times$ ULN (Grade 2)	
 • Continue all study treatment. • Monitor LFTs at least weekly. • Consider referral to a hepatologist and liver biopsy. • For suspected immune-related events of > 5 days duration 
 – Consider withholding atezolizumab^a – Consider administering 1–2 mg/kg/day oral prednisone or equivalent followed by ≥ 1 month taper – Restart atezolizumab if event resolves to Grade 1 or better within 105 days.^{b, c} – Permanently discontinue atezolizumab and cobimetinib if event does not resolve to Grade 1 or better within 105 days.^{a, b, c}
AST/ALT > $5 \times$ baseline values to < $10 \times$ ULN with total bilirubin < $2 \times$ ULN (Grade 3)	
 • Continue all study treatment. • Monitor LFTs at least weekly. • Consider referral to a hepatologist and liver biopsy. • For suspected immune-related events: 
 – Withhold atezolizumab – Consider administering 1–2 mg/kg/day oral prednisone or equivalent followed by ≥ 1 month taper – If event does not improve within 48 hours after initiating corticosteroids, consider adding an immunosuppressive agent. If event resolves to Grade 1 or better, taper corticosteroids over ≥ 1 month. – Permanently discontinue atezolizumab and cobimetinib if event does not resolve to Grade 1 or better within 105 days.^{a, b, c}

LFT = liver function test; Q4W = every 4 weeks; ULN = upper limit of normal.

^a Resumption of atezolizumab may be considered in patients who are deriving benefit and have fully recovered from the immune-related event. Patients can be rechallenged with atezolizumab only after approval has been documented by both the investigator (or an appropriate delegate) and the Medical Monitor.

^b If corticosteroids have been initiated, they must be tapered over ≥ 1 month to ≤ 10 mg/day oral prednisone or equivalent before atezolizumab can be resumed.

^c Atezolizumab may be withheld for a period of time beyond 105 days to allow for corticosteroids to be reduced to ≤ 10 mg/day oral prednisone or equivalent. The acceptable length of the extended period of time must be agreed upon by the investigator and the Medical Monitor.

Table 6 Guidelines for Management of Patients Who Experience Specific Adverse Events (Cobimetinib and Atezolizumab) (cont.)

Event	Action to Be take

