Elevations in ALT, AST, and/or bilirubin (cont.)	
AST/ALT > 3 × ULN with bilirubin > 2 × ULN	
 • Withhold atezolizumab and cobimetinib. • Consult hepatologist and consider liver biopsy. • Consider administering 1–2 mg/kg/day oral prednisone or equivalent followed by ≥ 1 month taper (for possible autoimmune hepatitis). • If LFTs do not decrease within 48 hours after initiation of systemic steroids, consider adding an immunosuppressive agent (e.g., mycophenolate mofetil or TNF-α antagonist). • Monitor LFTs every 48–72 hours until decreasing and then follow weekly. • Restart atezolizumab at fixed dose and cobimetinib at 1 dose reduction after discussion with Medical Monitor if AST/ALT < 3 × ULN with bilirubin < 2 × ULN and steroid dose < 10 mg oral prednisone equivalent per day.^{a, b, c} • Permanently discontinue atezolizumab and cobimetinib for life-threatening hepatic events, and contact the Medical Monitor.
AST/ALT > 10 × ULN	
 • Permanently discontinue atezolizumab and cobimetinib.^c • Consult hepatologist and consider liver biopsy. • Consider administering 1–2 mg/kg/day oral prednisone or equivalent (for possible autoimmune hepatitis). If event resolves to Grade 1 or better, taper corticosteroids over ≥ 1 month. • If LFTs do not decrease within 48 hours after initiation of systemic steroids, addition of an alternative immunosuppressive agent (e.g., mycophenolate mofetil or TNF-α antagonist) or dose escalation of corticosteroids may be considered. • Monitor LFTs every 48–72 hours until decreasing and then follow weekly.

LFT = liver function test; TNF-α = tumor necrosis factor–alpha; ULN = upper limit of normal.

^a If corticosteroids have been initiated, they must be tapered over ≥ 1 month to ≤ 10 mg/day oral prednisone or equivalent before atezolizumab can be resumed.

^b Atezolizumab may be withheld for a period of time beyond 105 days to allow for corticosteroids to be reduced to ≤ 10 mg/day oral prednisone or equivalent. The acceptable length of the extended period of time must be agreed upon by the investigator and the Medical Monitor.

^c Resumption of atezolizumab may be considered in patients who are deriving benefit and have fully recovered from the immune-related event. Patients can be rechallenged with atezolizumab only after approval has been documented by both the investigator (or an appropriate delegate) and the Medical Monitor.

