Treatment-emergent rash has been associated with atezolizumab. The majority of cases of rash were mild in severity and self limited, with or without pruritus. A dermatologist should evaluate persistent and/or severe rash or pruritus. A biopsy should be considered unless contraindicated. Management guidelines for dermatologic events are provided in [Table 9](#).

Table 9 Management Guidelines for Dermatologic Events

Event	Management
Dermatologic event, Grade 1	
 • Continue atezolizumab. • Consider treatment with topical corticosteroids and/or other symptomatic therapy (e.g., antihistamines).
Dermatologic event, Grade 2	
 • Continue atezolizumab. • Consider patient referral to dermatologist. • Initiate treatment with topical corticosteroids. • Consider treatment with higher-potency topical corticosteroids if event does not improve.
Dermatologic event, Grade 3	
 • Withhold atezolizumab for up to 12 weeks after event onset.^a • Refer patient to dermatologist. • Initiate treatment with 10 mg/day oral prednisone or equivalent, increasing dose to 1–2 mg/kg/day if event does not improve within 48–72 hours. • If event resolves to Grade 1 or better, resume atezolizumab.^b • If event does not resolve to Grade 1 or better while withholding atezolizumab, permanently discontinue atezolizumab and contact Medical Monitor.^c
Dermatologic event, Grade 4	
 • Permanently discontinue atezolizumab and contact Medical Monitor.^c

^a Atezolizumab may be withheld for a longer period of time (i.e., > 12 weeks after event onset) to allow for corticosteroids (if initiated) to be reduced to ≤ 10 mg/day oral prednisone or equivalent. The acceptable length of the extended period of time must be agreed upon by the investigator and the Medical Monitor.

^b If corticosteroids have been initiated, they must be tapered over ≥ 1 month to ≤ 10 mg/day oral prednisone or equivalent before atezolizumab can be resumed.

^c Resumption of atezolizumab may be considered in patients who are deriving benefit and have fully recovered from the immune-related event. Patients can be re-challenged with atezolizumab only after approval has been documented by both the investigator (or an appropriate delegate) and the Medical Monitor.

Appendix 8

Risks Associated with Atezolizumab and Guidelines for Management of Adverse Events Associated with Atezolizumab (cont.)

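### Table 6 (Cohorts A and B): the Grade 3 skin row sets two atezolizumab grades on one 105-day deadline, and the Grade 2 and 3 liver rows mix baseline and ULN limits, so they overlap or leave gaps

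*Combined protocol and SAP*

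**What the plan says.** **Skin.** In the Grade 3 dermatologic row of Table 6 (Section 5.1.3.3), both drugs are withheld. One bullet then reads "If event resolves to Grade 2 or better within 105 days, resume atezolizumab at fixed dose" and adds that otherwise both drugs stop for good. The next bullet reads "Permanently discontinue atezolizumab and cobimetinib and contact Medical Monitor if event does not resolve to Grade 1 or better within 105 days". The cobimetinib bullet reads "If event resolves to Grade 2 or better within 28 days, resume cobimetinib with dose reduced by one level". Two neighbouring rules bear on the choice of grade. The Table 6 row headed "Dermatologic event, Grade 1 or 2" continues both drugs. Appendix 8, Table 9, uses a stricter level after a Grade 3 skin event: "If event resolves to Grade 1 or better, resume atezolizumab".

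**Liver.** With total bilirubin below 2×ULN, Table 6 has three graded AST/ALT rows. The Grade 1 row runs from above ULN to 3×ULN. The Grade 2 row is defined as "AST/ALT > $3 \times$ baseline values to < $5 \times$ ULN". The Grade 3 row has the same form, with 5×baseline and 10×ULN. The Grade 2 and 3 rows both begin with "Continue all study treatment". Above 10×ULN the action is "Permanently discontinue atezolizumab and cobimetinib". Section 4.1.1.4 admits patients with AST/ALT up to 2.5×ULN, or up to 5×ULN with documented liver metastases.

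**The concern.** These are dosing instructions for a combination with known skin and liver toxicity, to be applied at about 60 centres (Section 9.4). The skin row gives opposite instructions for one clinical state. The liver rows give several instructions, or none, depending on the AST/ALT with which the patient entered. Sites can then handle the same event differently. For example, a patient who entered at 2×ULN and reaches 9×ULN (4.5×baseline) is in no graded row, and the next printed step is permanent discontinuation of both drugs above 10×ULN. What is at stake is patient safety and consistent conduct between sites.

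**Working it through.** The plan states no figure on this point, so there is none to reproduce. The check applies the printed rules to each possible state.

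**Skin: the two atezolizumab bullets at day 105**

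| State at day 105 | First bullet | Second bullet |
|---|---|---|
| Grade 1 or better | resume atezolizumab | no stop |
| Grade 2 | resume atezolizumab | stop both permanently |
| Grade 3 or worse | stop both permanently | stop both permanently |

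Only the middle line conflicts. The bullets could be read in sequence: restart at Grade 2, then stop if Grade 1 has not followed by day 105. The row does not say so. On that reading the first bullet's own stopping clause would decide nothing, because anything worse than Grade 2 already fails the second bullet.

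**Liver: inputs**

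Let b be baseline AST/ALT and x the current value, both in multiples of ULN, with bilirubin below 2×ULN. From Table 6:

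- Grade 1 row: 1 < x ≤ 3
- Grade 2 row: 3b < x < 5
- Grade 3 row: 5b < x < 10
- Stopping row: x > 10

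From Section 4.1.1.4: b ≤ 2.5, or b ≤ 5 with liver metastases.

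**Where the rows join.** Grades 1 and 2 meet when 3b = 3, and Grades 2 and 3 when 5b = 5. Both require b = 1. Even there, the strict inequalities leave exactly 5 and exactly 10×ULN in no row.

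**Overlap (b < 1).** At b = 0.5 the Grade 2 row is 1.5–5 and the Grade 3 row is 2.5–10. Values of 1.5–2.5 lie in Grades 1 and 2, values of 2.5–3 in all three, and values of 3–5 in Grades 2 and 3. All three rows overlap whenever 5b < 3, that is b < 0.6. The actions differ in two respects. Liver tests are every 4 weeks under Grade 1 but at least weekly under Grades 2 and 3. If an immune cause is suspected, atezolizumab is continued (Grade 1), considered for withholding after more than 5 days (Grade 2) or withheld (Grade 3).

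**Empty rows (b > 1).** The Grade 2 row is empty when 3b ≥ 5, so b ≥ 5/3 = 1.67. The Grade 3 row is empty when 5b ≥ 10, so b ≥ 2. Both thresholds lie inside the eligibility limits.

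**Gaps, counted conservatively.** Treat any x at or below 3b as not yet triggered, and count only uncovered values above 3b, as a share of the 3–10×ULN span (length 7):

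| b | Grade 2 row | Grade 3 row | Uncovered above 3b | Share of 7 |
|---|---|---|---|---|
| 1.25 | 3.75–5 | 6.25–10 | 5–6.25 = 1.25 | 18% |
| 1.5 | 4.5–5 | 7.5–10 | 5–7.5 = 2.5 | 36% |
| 1.75 | empty | 8.75–10 | 5.25–8.75 = 3.5 | 50% |
| 2 | empty | empty | 6–10 = 4 | 57% |
| 2.5 | empty | empty | 7.5–10 = 2.5 | 36% |
| ≥ 3.33 | empty | empty | none (3b ≥ 10) | 0% |

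**Two consequences at high baselines.** Above b = 3.33 the stopping row is reached before 3×baseline; at b = 5 it is reached at 10/5 = 2×baseline. Above b = 3 the patient's own starting value is higher than the top of the Grade 1 row (3×ULN), yet resolution is defined as Grade 1 or better.

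**The case against.** **Not yet triggered.** The Grade 2 row starts at 3×baseline, and Sections 5.2.3 and 5.3.5.7 use the same multiple for reportable liver injury. A reader might infer that every value between 3 and 10×ULN lacks an instruction once baseline reaches 2×ULN. The documents do not support that. For an abnormal baseline, a value below 3×baseline can reasonably be read as calling for no change. This objection stands, which is why the shares above exclude such values. It does not close the remaining gaps.

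**Small default consequence.** All three graded rows continue both drugs by default, and Section 5.3.3 mandates NCI CTCAE v4.0. Following the grade labels alone would settle much of the overlap. That is fair, but the printed baseline limits would then have no function, and no text tells sites to ignore them.

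**Other text fills the gaps.** A reader might infer that Table 5 or the last row of Table 6 applies to a gap value and gives a stricter action than the Grade 3 liver row. That is weak. Section 5.1.3.1 calls Table 5 general and sends specific events to Table 6, and the last row is limited to treatment-related toxicities that the table has not already covered.

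**Conflict with other sections.** A reader might infer a further contradiction with Section 5.1.1.1.5 and Appendix 8, Table 2, on Grade 3 AST/ALT. The first is a risk description tied to use with vemurafenib. For the second, both sources allow approved rechallenge. Declaring that Table 6 always prevails would select the less conservative action (withhold rather than stop) for suspected immune-related Grade 3 hepatitis, without a clinical reason.

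**Skin timing.** A reader might infer that a patient could restart atezolizumab early at Grade 2 and then be stopped on day 105 without worsening. If corticosteroids were used, footnote a requires a taper of at least 1 month before restart. The general guidance in Table 6 also treats 105 days as a limit on withholding. Neither point resolves the two grades.

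**Conclusion.** The concern holds for two rules in Table 6. The skin row is contradictory for an event at Grade 2 on day 105. The liver rows form a consistent scale only at a baseline of 1×ULN. On the conservative count, 18%, 36%, 50% and 57% of the 3–10×ULN span has no row at baselines of 1.25, 1.5, 1.75 and 2×ULN; the share falls to 36% at 2.5 and to 0% from 3.33.

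These results assume bilirubin below 2×ULN. Above 2×ULN, a separate row covers AST/ALT over 3×ULN whatever the baseline. The shares describe a numerical range, not patients; the number of patients affected cannot be derived from the documents. Pre-dose laboratory checks (Section 4.4) and 24-hour reporting of significant liver toxicity (Section 5.2.3) limit the harm, but neither says which row applies.

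A reader might infer that the efficacy results are compromised. Nothing in Section 6 supports that: the analysis population, endpoints and intervals do not depend on these rules. This is a safety and conduct fault that should be corrected.

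**What to change.** **Skin row.** Use one resume/stop grade for atezolizumab. Grade 1 would match the stopping bullet and Appendix 8, Table 9. Grade 2 would match the cobimetinib bullet and the Table 6 row that continues both drugs at Grade 1 or 2. The sponsor's clinicians should choose.

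**Liver rows.** Set both limits of each row, and the level that counts as resolution, on one reference: ULN if baseline is normal, multiples of baseline if it is abnormal. Each value should fall in exactly one row, boundary values included. State whether the stopping row above 10×ULN stays on ULN for patients with an abnormal baseline.

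**Cost.** These are dose-modification rules, so Section 9.6 requires IRB/EC approval and, where locally required, regulatory approval before use; revised consent forms may follow under Section 8.2. No new procedures, visits or analyses are needed.

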5.1.3.3 Management of Cobimetinib- and Atezolizumab-Specific Adverse Events

Toxicities associated or possibly associated with cobimetinib plus atezolizumab treatment should be managed according to standard medical practice. See [Appendix 8](#) for management of adverse events related to atezolizumab.

For management of cobimetinib- and atezolizumab-specific toxicities, including IRRs, gastrointestinal toxicity, dermatologic toxicity, hepatotoxicity, pulmonary toxicity, potential eye toxicity, reductions in LVEF from baseline, rhabdomyolysis, elevated CPK, and hemorrhage, see [Table 6](#).

Table 6 Guidelines for Management of Patients Who Experience Specific Adverse Events (Cobimetinib and Atezolizumab)

Event	Action to Be Taken

General guidance for dose modifications and treatment delays and discontinuation
	
 • There will be no dose modifications for atezolizumab. • If atezolizumab is withheld and corticosteroids are initiated for an atezolizumab-related toxicity, corticosteroids must be tapered over ≥ 1 month to ≤ 10 mg/day oral prednisone or equivalent before atezolizumab can be resumed.^{a, b, c} 
The dose of cobimetinib can be reduced by 20 mg (one dose level) up to two times (i.e., from 60 mg to 40 mg and then from 40 mg to 20 mg). If further dose reduction is indicated after two dose reductions, the patient must discontinue cobimetinib but may continue treatment with atezolizumab at the investigator's discretion.
 
 • If atezolizumab is discontinued, treatment with cobimetinib may be continued at the investigator's discretion and after discussion with the Medical Monitor. • If cobimetinib is withheld for > 28 days because of toxicity, the patient should be discontinued from cobimetinib, unless resumption of treatment is approved by the Medical Monitor after discussion with the investigator. • If atezolizumab is withheld for > 105 days because of toxicity, the patient should be discontinued from atezolizumab, unless resumption of treatment is approved by the Medical Monitor after discussion with the investigator.

IRRs, anaphylaxis, and hypersensitivity reaction
	
 • Guidelines for management of IRRs are provided in Appendix 8. • For anaphylaxis precautions, see Appendix 7. • For severe hypersensitivity reactions, permanently discontinue all study treatment.

IRR=infusion-related reaction.

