Diarrhea, Grade 2 (intolerable) or Grade 3	
 • Withhold atezolizumab and cobimetinib. • Initiate supportive care and monitor patient closely. • Discontinue medications that may exacerbate colitis (e.g., NSAIDs) while investigating etiology. • Investigate etiology, referring patient to GI specialist for evaluation of possible colitis, including biopsy if appropriate. • If event resolves to Grade 1 or better within 105 days, resume atezolizumab at fixed dose. If not, permanently discontinue atezolizumab and cobimetinib.^{a, b, c} • If event resolves to Grade 1 or better within 28 days, resume cobimetinib with dose reduced by one level. If not, permanently discontinue cobimetinib.
Diarrhea, Grade 4	
 • Permanently discontinue atezolizumab and cobimetinib, and contact Medical Monitor.^c • Initiate supportive care and monitor patient closely. • Discontinue medications that may exacerbate colitis (e.g., NSAIDs) while investigating etiology. • Rule out bowel perforation. • Investigate etiology, referring patient to GI specialist for evaluation of possible colitis, including biopsy if appropriate.
Colitis, Grade 1	
 • Continue atezolizumab and cobimetinib. • Initiate supportive care and monitor patient closely. • Discontinue medications that may exacerbate colitis (e.g., NSAIDs). • Refer patient to GI specialist for evaluation and confirmatory biopsy if symptoms persist for > 7 days.

GI = gastrointestinal; NSAID = non-steroidal anti-inflammatory drug.

^a If corticosteroids have been initiated, they must be tapered over ≥ 1 month to ≤ 10 mg/day oral prednisone or equivalent before atezolizumab can be resumed.

^b Atezolizumab may be withheld for a period of time beyond 105 days to allow for corticosteroids to be reduced to ≤ 10 mg/day oral prednisone or equivalent. The acceptable length of the extended period of time must be agreed upon by the investigator and the Medical Monitor.

^c Resumption of atezolizumab may be considered in patients who are deriving benefit and have fully recovered from the immune-related event. Patients can be rechallenged with atezolizumab only after approval has been documented by both the investigator (or an appropriate delegate) and the Medical Monitor.

Table 6 Guidelines for Management of Patients Who Experience Specific Adverse Events (Cobimetinib and Atezolizumab) (cont.)

Event	Action to Be Taken
Gastrointestinal toxicity (cont.)	

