Table 6 Guidelines for Management of Patients Who Experience Specific Adverse Events (Cobimetinib and Atezolizumab) (cont.)

Event	Action to Be take
Pulmonary events	
General guidance	Mild-to-moderate events of pneumonitis have been reported with atezolizumab and cobimetinib. All pulmonary events should be thoroughly evaluated for other commonly reported etiologies such as pneumonia/infection, lymphangitic carcinomatosis, pulmonary embolism, heart failure, chronic obstructive pulmonary disease, or pulmonary hypertension. For events concerning for pneumonitis, consider comprehensive infectious evaluation including viral etiologies.
Pneumonitis, Grade 1 (asymptomatic)	
 • Continue atezolizumab and cobimetinib. • Re-evaluate on serial imaging. • Consider patient referral to pulmonary specialist.
Pneumonitis, Grade 2	
 • Withhold atezolizumab and cobimetinib. • Refer patient to pulmonary and infectious disease specialists and consider bronchoscopy or BAL. • If bronchoscopy is consistent with immune-related etiology, initiate treatment with 1–2 mg/kg/day oral prednisone or equivalent. • Resume atezolizumab and cobimetinib if event resolves to Grade 1 or better within 105 days.^{a, b} • Permanently discontinue atezolizumab and cobimetinib and contact Medical Monitor if event does not resolve to Grade 1 or better within 105 days.^{a, b, c} • For recurrent events, treat as a Grade 3 or 4 event.
Pneumonitis, Grade 3 or 4	
 • Permanently discontinue atezolizumab and cobimetinib.^c • Refer patient to pulmonary and infectious disease specialists and consider bronchoscopy or BAL. • If bronchoscopy is consistent with immune-related etiology, initiate treatment with 1–2 mg/kg/day oral prednisone or equivalent. • If pulmonary event does not improve within 48 hours or worsens, consider adding an immunosuppressive agent (e.g., infliximab, cyclophosphamide, IVIg, or mycophenolate). • If event resolves to Grade 1 or better, taper corticosteroids over ≥ 1 month.

BAL = bronchoscopic alveolar lavage; IVIg = intravenous immunoglobulin.

^a If corticosteroids have been initiated, they must be tapered over ≥ 1 month to ≤ 10 mg/day oral prednisone or equivalent before atezolizumab can be resumed.

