For Grade 4 CPK elevations that are asymptomatic and deemed not clinically significant	
 • Interrupt cobimetinib and atezolizumab treatment. • If improved to Grade ≤ 3 within 4 weeks, restart cobimetinib at a dose reduced by 20 mg, if clinically indicated. • If CPK elevations do not improve to Grade ≤ 3 within 4 weeks following dose interruption, permanently discontinue cobimetinib treatment. • Resumption of atezolizumab may be considered in patients who are deriving benefit.
Rhabdomyolysis or symptomatic CPK elevations	
 • Interrupt cobimetinib and atezolizumab treatment. • If severity is improved by at least one grade and symptoms resolve within 4 weeks, restart cobimetinib at a dose reduced by 20 mg, if clinically indicated. • If rhabdomyolysis or symptomatic CPK elevations do not improve within 4 weeks, permanently discontinue cobimetinib treatment • Resumption of atezolizumab may be considered in patients who are deriving benefit after discussion with the Medical Monitor.

CPK = creatine phosphokinase.

Table 6 Guidelines for Management of Patients Who Experience Specific Adverse Events (Cobimetinib and Atezolizumab) (cont.)

Event	Action to Be Taken
Hemorrhage	
Grade 3 hemorrhage	
 Interrupt cobimetinib treatment. There are no data on the effectiveness of cobimetinib dose modification for hemorrhage events. Clinical judgment should be applied when considering restarting cobimetinib treatment. Continue atezolizumab treatment.
Grade 4 hemorrhage or any grade cerebral hemorrhage	
 Interrupt cobimetinib treatment. Permanently discontinue cobimetinib for hemorrhage events attributed to cobimetinib. Continue atezolizumab treatment.
Grade 3 or 4 or intolerable Grade 2 treatment-related toxicities not described above and in Table 5 (dose modifications for cobimetinib)	
 Withhold all study treatment. If event resolves to Grade 1 or better within 105 days, resume atezolizumab at fixed dose. If not, permanently discontinue atezolizumab.^{a, b, c} If event resolves to Grade 1 or better within 28 days, resume cobimetinib with dose reduced by one level. If not, permanently discontinue cobimetinib.

^a If corticosteroids have been initiated, they must be tapered over ≥ 1 month to ≤ 10 mg/day oral prednisone or equivalent before atezolizumab can be resumed.

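### Table 6 lets cobimetinib restart up to day 105 after Grade 2 pneumonitis, although its general rule stops cobimetinib after 28 days unless the Medical Monitor approves

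*Combined protocol and SAP*

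**What the plan says.** Table 6 in Section 5.1.3.3 opens with general guidance that gives each drug its own limit on time off treatment.

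- Cobimetinib: "If cobimetinib is withheld for > 28 days because of toxicity, the patient should be discontinued from cobimetinib", followed by the exception "unless resumption of treatment is approved by the Medical Monitor after discussion with the investigator".
- Atezolizumab: "If atezolizumab is withheld for > 105 days because of toxicity, the patient should be discontinued from atezolizumab", with the same exception.

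Further down, the row for Grade 2 pneumonitis withholds both drugs and then says: "Resume atezolizumab and cobimetinib if event resolves to Grade 1 or better within 105 days". Its next bullet says: "Permanently discontinue atezolizumab and cobimetinib and contact Medical Monitor if event does not resolve to Grade 1 or better within 105 days". That is the only place where the row brings in the Medical Monitor, and it applies only when the event has not resolved by day 105.

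Three footnotes attach to the row. The first requires a steroid taper of at least a month before atezolizumab restarts. The second allows atezolizumab holds beyond 105 days by agreement with the Medical Monitor. The third requires documented approval for atezolizumab rechallenge. None of them concerns cobimetinib.

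**The concern.** The row applies the atezolizumab window to both drugs. A site that reads only the row could restart cobimetinib at any time up to day 105 without asking anyone, while the general guidance treats day 28 as the point after which cobimetinib stops unless the Medical Monitor agrees otherwise.

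What is at stake is re-exposure after symptomatic lung toxicity. Pneumonitis is listed as an important identified risk of cobimetinib (Section 5.1.1.1.6), and Table 6 notes reports of it with both drugs. The approval step is the safeguard for late restarts, and this row omits it. Response rates and the other efficacy estimates are not at issue.

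**Working it through.** The check is mainly a comparison of texts. The plan gives no figure of its own to reproduce.

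**Step 1: where the two texts diverge.** Assume both clocks start when the drugs are withheld.

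- Resolution by day 28, with cobimetinib restarted by then: the row and the general rule agree.
- Resolution on days 29 to 105: cobimetinib has been off for more than 28 days. The row says restart; the general rule says discontinue unless approved. The span is 105 − 28 = 77 days.
- Resolution after day 105: the row stops both drugs.

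The row's own steroid path can also lead past day 28. If bronchoscopy points to an immune-related cause, the row starts prednisone, and atezolizumab then waits for a taper of at least a month. A site that restarts the two drugs together, as the joint bullet reads, would normally be past day 28 for cobimetinib even if the event had resolved sooner.

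**Step 2: what the rest of Table 6 does with cobimetinib.**

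| Row | Time condition for restarting cobimetinib |
|---|---|
| Diarrhea, intolerable Grade 2 or Grade 3 | 28 days |
| Colitis, Grade 2 | 28 days |
| Colitis, Grade 3 | 28 days |
| Dermatologic event, Grade 3 | 28 days |
| CPK elevation, Grade 4 | 4 weeks |
| Rhabdomyolysis or symptomatic CPK elevation | 4 weeks |
| Toxicities not otherwise listed | 28 days |
| **Pneumonitis, Grade 2** | **105 days** |

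Seven rows use 28 days or 4 weeks; one uses 105 days. The wording of the seven is clear. The diarrhea row, once its 28-day condition is met, says "resume cobimetinib with dose reduced by one level. If not, permanently discontinue cobimetinib", and the Grade 4 CPK row says "If improved to Grade ≤ 3 within 4 weeks, restart cobimetinib at a dose reduced by 20 mg, if clinically indicated". These rows are stricter than the general rule, since they stop cobimetinib after the limit and mention no exception.

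The remaining rows do not compete:

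- Raised AST/ALT with raised bilirubin has no day limit but does involve the monitor: "Restart atezolizumab at fixed dose and cobimetinib at 1 dose reduction after discussion with Medical Monitor".
- Serous retinopathy and the two hemorrhage rows set no day limit for a cobimetinib restart, which leaves the general rule in force.
- The LVEF rows use fixed breaks of 2 or 4 weeks.
- The Grade 2 and Grade 3 AST/ALT rows mention cobimetinib at 105 days, but only to discontinue it; they do not withhold it at the start.

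An explicit cobimetinib window longer than 28 days therefore appears only in the Grade 2 pneumonitis row.

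**Step 3: how many patients.** Inputs:

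- Patients who receive cobimetinib: about 102 (Cohorts A and B, Section 6.1). Cohort C receives none.
- Pneumonitis rate: 1.6% at any grade, none of Grade 3 or higher, with cobimetinib plus vemurafenib (Section 5.1.1.1.6). The documents give no Grade 2 rate for cobimetinib plus atezolizumab.
- Assumptions with no source in the documents: an any-grade rate of up to 5%, and 10% to 50% of cases being Grade 2 with cobimetinib held for more than 28 days.

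Expected number = patients × rate × share. Chance of at least one = 1 − (1 − rate × share)^102.

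- Documented rate, every case counted: 102 × 0.016 × 1 = 1.63 patients.
- Low: 102 × 0.016 × 0.10 = 0.16 patients; 1 − (1 − 0.0016)^102 = 0.151, or 15%.
- High: 102 × 0.05 × 0.50 = 2.55 patients; 1 − (1 − 0.025)^102 = 0.924, or 92%.

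**The case against.** The strongest reply is that there is no true contradiction. General guidance at the head of a table governs the rows below it unless a row opts out, and this row does not waive approval. The two rules also measure different things: the row sets a deadline for the event to resolve, the general guidance a limit on time off drug. A site can obey both by restarting within 105 days and obtaining approval if cobimetinib was off for more than 28. On this view only a cross-reference is missing. The seven stricter rows are also silent on the exception, so silence should count alike everywhere.

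That reading is available, and it is probably what the sponsor intends. It does not dispose of the point. The row is not silent: it gives a positive instruction to restart cobimetinib inside a window that the general guidance assigns to the other drug. The stricter rows err on the side of stopping, so following one of them alone cannot lead to an unapproved late restart. Following this row alone can.

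Three further objections have some force.

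- Pneumonitis is an adverse event of special interest, reportable within 24 hours (Section 5.2.3), and the row calls for specialist referral. The sponsor would hear of each case. Reporting onset is not the same as approving a restart weeks later.
- The patient range is wide and rests on assumed inputs. It counts holds longer than 28 days, not restarts without approval. If every site applied the general rule, unapproved restarts would be zero.
- Table 5 does not settle the restart dose. Its tolerable Grade 2 line keeps the dose at 60 mg but describes dosing that continues; its intolerable Grade 2 line interrupts and restarts at 40 mg. The correction should not try to decide this.

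**Conclusion.** The concern holds as a minor internal inconsistency in the safety rules, wrong as written. The Grade 2 pneumonitis row gives cobimetinib a window that the same table reserves for atezolizumab and omits the approval that the general rule requires after day 28. The isolation of this row among the day-limited rows suggests a slip rather than a deliberate exception; that is an inference, and the documents offer no reason for a longer window.

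Few patients are likely to be involved. The figure of 1.63 is an expected count at a rate borrowed from a different combination, not a hard maximum. The range of 0.16 to 2.55 depends on the unsourced 5% rate and 10% to 50% share. The conflict in the text depends on none of these numbers, and no efficacy estimate changes.

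**What to change.** Replace the joint bullet in the Grade 2 pneumonitis row with one for each drug:

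- Atezolizumab: restart once the event is down to Grade 1 or lower, provided this happens by day 105. The two existing footnotes stay.
- Cobimetinib: restart once the event is down to Grade 1 or lower, provided this happens by day 28. If cobimetinib has been off for more than 28 days, restart only with Medical Monitor approval under the general guidance; otherwise discontinue it.

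The restart dose stays with Table 5 and the sponsor's clinical judgment, with no mandatory reduction added. The cost is a wording change to one bullet. It restores the sponsor's own rule and changes nothing in data collection, sample size or analysis.
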